Subjects were randomized in double-blind, counterbalanced, placebo-controlled fashion to either placebo or a single 200mg dose of tolcapone on their first visit and the alternative treatment on their second visit. After receiving task instructions and undergoing a brief practice session of 10-20 trials, subjects performed the delay discounting task (Figure 1) within the MRI scanner while blood-oxygen level dependent (BOLD) images were obtained. Subjects entered the MRI scanner 90 minutes after drug ingestion to ensure that the delay discounting task was performed while drug levels were at peak (approximately 120 minutes: tolcapone package insert, Valeant Pharmaceuticals). The 256 total trials were presented in pseudorandom order. At the start of each trial, subjects were cued to one of four trial types: Want (W), Don't Want (DW), Sooner (S), and Larger (L) (see below). For each of these trial types, subjects were then presented with two hypothetical alternatives: a smaller amount of money available today ("Now") and a larger amount available later ("Later"). We have previously shown that this paradigm with hypothetical rewards effectively engages subjects (Boettiger et al., 2007; Boettiger et al., 2009), consistent with reports that hypothetical rewards activate common brain regions involved in value computations (Kang et al., 2011). As in our previous work (Boettiger et al., 2007), the 'Later' option consisted of six amounts (\$1, \$2, \$5, \$10, \$20, or \$100) at one of five future delays (1 week, 2 weeks, 1 month, 3 months, or 6 months). The percentage difference between the Now and Later options was selected from one of four different values (30%, 15%, 10%, and 5%). Subjects then made a button press to select one of the two options, randomly assigned to

the left and right sides of the screen.

Each of the four trial types allowed us to investigate different functions. In the W condition, the primary analytic focus of this study, subjects chose the option they preferred. In the DW condition, subjects also chose the option they preferred, but then made a button-press to select the opposite choice. This condition permitted us to evaluate motor impulsivity by comparing the proportion of responses in the W and DW conditions. In the S and L conditions, which we combined to form a control (CON) condition, subjects simply selected the sooner or larger options, respectively. These trial types allowed us to ensure that subjects were appropriately following instructions, and to introduce a condition in which the decision about monetary options was not a motivated choice. The W condition comprised half of all trials; the CON conditions comprised one-third; and the DW condition comprised one-sixth. As expected, subjects performed very well in the CON condition (accuracy = 0.97 ± 0.008 (sem)) and therefore we do not further report results of the CON condition in this paper.

The primary behavioral outcome was the impulsive choice ratio (ICR), which represents the ratio of the number of sooner choices to the number of total choices in the W condition. As in our previous work, we calculated a number of related measures of impulsive choice, including a measure of the hyperbolic discounting rate (k) and the interest rate differentiating the two choices. Because values such as the hyperbolic discounting rate were highly correlated with ICR (e.g. $r(\text{ICR}, k) = 0.78$, $p < 1 \times 10^{-5}$) and consequently gave qualitatively similar results, we elected to study the simplest, most intuitive quantity, as in our previous work (Boettiger et al.,

2007; Boettiger et al., 2009). ICR values underwent an arcsine-square root transform – i.e. were variance-stabilized – to permit the application of parametric statistical tests.

Both before drug administration and after the scanner run, subjects completed a speeded responding task to assess potential changes in motor function on and off tolcapone. Subjects were required to make a button press response as soon as possible after the presentation of either a brief visual or auditory stimulus. Reaction times were compared both within each session and across the tolcapone and placebo conditions. Due to computer failures, these data were available for only 19 of our 23 subjects.

MRI image acquisition

MRI scanning was conducted on a Siemens MAGNETOM Trio 3T MR Scanner at the Henry H. Wheeler, Jr. Brain Imaging Center at the University of California, Berkeley. Anatomical images consisted of 160 slices acquired using a T1-weighted MP-RAGE protocol (TR = 2300 ms, TE = 2.98 ms, FOV = 256 mm, matrix size = 256 x 256, voxel size = 1 mm³). Functional images consisted of 24 slices acquired with a gradient echoplanar imaging protocol (TR = 1370 ms, TE = 27 ms, FOV = 225 mm, matrix size = 96 x 96, voxel size = 2.3 x 2.3 x 3.5 mm). A projector (Avotec SV-6011, <http://www.avotec.org>) was used to display the image on a translucent screen placed within the scanner bore behind the head coil. A mirror was used to allow the subject to see the display. Subjects made their responses via an MRI-safe fiber optic response pad (Inline Model HH-1x4-L, <http://www.crsLtd.com>).

fMRI preprocessing

fMRI preprocessing was performed using both the AFNI (<http://afni.nimh.nih.gov>) and FSL (<http://www.fmrib.ox.ac.uk/fsl/>) software packages. Functional images were converted to 4D NIfTI format and corrected for slice-timing offsets. Motion correction was carried out using the AFNI program *3dvolreg*, with the reference volume set to the mean image of the first run in the series. Images were then smoothed with a 5mm FWHM Gaussian kernel. Co-registration was performed with the AFNI program *3dAllineate* using the local Pearson correlation cost function optimized for fMRI-to-MRI structural alignment. The subsequent inverse transformation was used to warp the anatomical image to the functional image space. Anatomical images were normalized to a standard volume (MNI_N27) using the FSL program *fnirt* available from the Montreal Neurological Institute (MNI; <http://www.bic.mni.mcgill.ca>). The same normalization parameters were later applied to native-space statistical maps as necessary for the generation of group statistical maps (see below).

Univariate analysis

To address a series of hypotheses, we carried out a number of voxel-wise fMRI statistical analyses for each subject using the general linear model (GLM) framework implemented in the AFNI program *3dDeconvolve*. The BOLD correlates of different decisions were assessed by modeling the cue and decision phases of the task for the four different conditions (Want, Don't Want, Sooner, Larger) with separate regressors, each of which was derived by convolving a gamma probability density function (peaking at 6 seconds) with a vector of stimulus onsets for each condition. Map-wise significance ($p < 0.05$, corrected for multiple comparisons) was determined by applying a cluster-size correction derived from the AFNI programs *3dFWHMx* and *3dClustSim* on data initially thresholded at a value of $p < 0.005$ (uncorrected). For the main

effect of task (figure 3), a whole-brain correction was applied. This contrast compared event onsets from all conditions – including both cue and outcome – with baseline fMRI activity on tolcapone versus placebo to illustrate that there are widespread changes in BOLD signal across the brain resulting from the use of tolcapone. Because cortical dopamine projections are frontally predominant (Cools, 2008), subsequent univariate analyses designed to address more specific task-related hypotheses about changes in frontostriatal regions used the AAL template brain (Tzourio-Mazoyer et al., 2002) to generate a frontostriatal mask (AAL areas 3-32 and 71-76; analyses illustrated in figures 4 and 5a).

Multivariate analysis

Resting state data were used to evaluate the connectivity between brain regions in both the tolcapone and placebo conditions in all subjects who completed both resting state sessions (N = 22; due to technical failures, complete resting state data from one of our 23 subjects were not obtained). This approach allowed us to identify any drug-related changes in connectivity independent of task performance. These data were smoothed by a 2.5mm FWHM Gaussian kernel prior to temporal bandpass filtering between 0.009 Hz and 0.08 Hz to reduce the influence of cardiac and respiratory artifact, per the protocol of Fox and colleagues (Fox et al., 2005). Movement parameters and the white matter and ventricular time series, but not the global mean signal, were included as regressors of no interest. A striatal region of interest in the left ventral putamen was chosen, based on the results of our univariate analyses (see Results, Figure 4a). A time course defined by averaging across voxels in this region was then correlated with every other voxel in the brain, and correlation coefficients were Fisher-transformed to allow for the application of parametric statistical tests. Images were then normalized to the MNI template

prior to the application of group-level statistics. Because of our hypotheses about changes in frontostriatal connectivity, data were masked with a prefrontal mask (AAL regions 3-32) before the appropriate cluster-size correction was calculated.

For the evaluation of connectivity during task performance, we used the seed region (left ventral putamen) and significantly-connected region (left pregenual anterior cingulate cortex) identified in the resting state connectivity analysis shown in Figure 5b. For each of these two ROIs, the time series for each of the eight task-state runs was windowed with a 4-point split-cosine bell and concatenated with the other segments to produce a subject-specific time series. Time series within each ROI were then averaged across voxels to generate a single time series for each ROI. Coherency values were obtained by applying a fast Fourier transform (Matlab, <http://www.mathworks.com>) to the data for each pair of ROIs, implemented via Welch's periodogram averaging method using a 64-point discrete Fourier transform, Hanning window, and overlap of 32 points (Kayser et al., 2009). Coherence values for each ROI were then computed using the band-averaged coherence. To compute correlations between coherence results and other values, we first Fisher-transformed the coherence values to generate an approximately normal distribution (Rosenberg et al., 1989) that permitted us to apply parametric statistical tests.

Statistical Analysis

For analysis of behavioral data, paired T-tests and Pearson's correlation coefficients were used to calculate statistical significance. For univariate and multivariate analyses of BOLD data, significance was calculated using statistical techniques and corrections implemented in the Afni

software package, including the functions *3dDeconvolve*, *3dFWHMx*, *3dClustSim*, and *3dttest++*.

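### The map-wise p < 0.05 relies on an estimated smoothness and an assumed noise shape; sign-flip permutation of the drug-difference maps would remove both assumptions at little cost

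*Combined protocol and SAP*

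**What the plan says.** The Univariate analysis section states that map-wise significance at p < 0.05, corrected, "was determined by applying a cluster-size correction derived from the AFNI programs *3dFWHMx* and *3dClustSim* on data initially thresholded at a value of" (the forming value is p < 0.005, uncorrected). Two search volumes follow. For the main "effect of task (figure 3), a whole-brain correction was applied"; that contrast is tolcapone against placebo, and its stated purpose is "to illustrate that there are widespread changes in BOLD signal across the brain resulting from the use of tolcapone". More specific hypotheses are tested in a frontostriatal mask ("AAL areas 3-32 and 71-76; analyses illustrated in figures 4 and 5a").

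For the resting-state map, the Multivariate analysis section says "These data were smoothed by a 2.5mm FWHM Gaussian kernel" and then applies a cluster-size correction within a prefrontal mask (AAL 3-32). No forming threshold is given for that map specifically. Its seed, the left ventral putamen, "was chosen, based on the results of our univariate analyses" (Figure 4a). The coherence analysis then uses this seed together with the left pregenual cingulate region found in Figure 5b.

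The acquisition grid is given as "matrix size = 96 x 96, voxel size = 2.3 x 2.3 x 3.5 mm". Under fMRI preprocessing, "The same normalization parameters were later applied to native-space statistical maps as necessary for the generation of group statistical maps"; the group grid is not stated. The supplied text gives the applied kernels (5 mm task, 2.5 mm rest). It does not give the estimated smoothness, the spatial noise model, the resulting cluster extents or the sidedness. No permutation test is described.

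**The concern.** A simulated cluster extent answers one question: how large a cluster arises by chance in noise of this shape and this smoothness? If real noise has longer spatial tails than the simulated noise, or is smoother than estimated, chance clusters are larger than the simulation expects and the true map-wise error exceeds 5%.

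What is at stake is the chain of regions. The Figure 4a cluster sets the seed, the seed produces the Figure 5b cluster, and both become the regions for task coherence. A chance cluster early in that chain would weaken the frontostriatal interpretation of the later steps. The primary behavioural outcome (impulsive choice ratio, paired t-test) does not use these maps.

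**Working it through.** **The plan's own figure.** The stated 5% cannot be reproduced, because the supplied text lacks the smoothness, noise model, mask sizes, sidedness and extents. The check is therefore a simulation of how far the level moves under assumed values.

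**Inputs from the documents.** n = 23 (task) and 22 (rest); forming p < 0.005; in-plane voxel 225/96 = 2.34 mm; slice 3.5 mm. Voxel volume = 2.34375² × 3.5 = 19.23 mm³.

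**Inputs assumed.** Brain 66,352 voxels (× 19.23 mm³ = 1,276 mL); masks 24,352 (468 mL) and 12,608 (242 mL). Gaussian noise FWHM 5.83 mm (task) and 3.9 mm (rest). In the mild tail, 20% of the spatial correlation is exponential with 10 mm scale; in the heavy tail, 40% with 12 mm scale. The test is two-sided with each sign clustered separately and face-connected voxels. For rest, forming p < 0.005 is itself an assumption.

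**Method.** Take the smallest extent k with P(largest cluster ≥ k) ≤ 0.05 in Gaussian fields matched on smoothness. Apply k to null group t-maps and count the maps with any surviving cluster. Sign-flipping (99 flips) was run on the same acquisition-grid datasets.

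**Task maps, n = 23** (false-positive maps / datasets):

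| Map and method | Gaussian | Mild tail | Heavy tail |
|---|---|---|---|
| Larger mask, simulated k, acquisition grid | 4/180 = 0.02 | 13/240 = 0.05 | 34/240 = 0.14 |
| Larger mask, simulated k, 2 mm grid | 5/180 = 0.03 | 24/240 = 0.10 | 34/240 = 0.14 |
| Larger mask, sign-flip | 4/180 = 0.02 | 9/240 = 0.04 | 16/240 = 0.07 |
| Smaller mask, simulated k, acquisition grid | 1/180 = 0.01 | 11/240 = 0.05 | 18/240 = 0.08 |
| Smaller mask, simulated k, 2 mm grid | 2/180 = 0.01 | 14/240 = 0.06 | 21/240 = 0.09 |
| Smaller mask, sign-flip | 4/180 = 0.02 | 7/240 = 0.03 | 11/240 = 0.05 |
| Whole brain, simulated k, acquisition grid | 2/180 = 0.01 | 17/240 = 0.07 | 53/240 = 0.22 |
| Whole brain, simulated k, 2 mm grid | 5/180 = 0.03 | 38/240 = 0.16 | 61/240 = 0.25 |
| Whole brain, sign-flip | 9/180 = 0.05 | 12/240 = 0.05 | 12/240 = 0.05 |

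Exact 95% intervals: 13/240 gives 0.029-0.091, which includes 0.05; 34/240 gives 0.100-0.192, which does not; the highest sign-flip count, 16/240, gives 0.039-0.106, which includes 0.05.

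**Smoothness understated by 10%, Gaussian noise.** Whole brain 14/180 = 0.08 (0.043-0.127); masks 9/180 = 0.05 (0.023-0.093) and 4/180 = 0.02.

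**Resting map, n = 22** (larger / smaller mask). Simulated k: Gaussian 1/120 and 2/120 (0.01, 0.02); mild 9/180 and 10/180 (0.05, 0.06); heavy 21/180 and 15/180 (0.12, 0.08). Sign-flip: 5/120 and 2/120 (0.04, 0.02); 7/180 and 8/180 (0.04, 0.04); 10/180 and 7/180 (0.06, 0.04).

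**Second simulation, different assumptions.** About 20,000 voxels, one-sided, FWHM near 6 mm, exponential scale 10 mm, n = 23, 600 datasets per case:

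| Gaussian share of the correlation | Simulated k (95% CI) | Sign-flip (95% CI) |
|---|---|---|
| 1.0 | 0.022 (0.012-0.037) | 0.030 (0.018-0.047) |
| 0.9 | 0.035 (0.022-0.053) | 0.038 (0.024-0.057) |
| 0.7 | 0.092 (0.070-0.118) | 0.042 (0.027-0.061) |
| 0.5 | 0.152 (0.124-0.183) | 0.042 (0.027-0.061) |

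In the same setting, the Gaussian extent needed for 5% rises from 10 voxels at 4 mm FWHM to 25 at 6 mm and 77 at 10 mm.

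**Feasibility.** Sign patterns available: 2^23 = 8,388,608 (task) and 2^22 = 4,194,304 (rest), so a random sample of a few thousand flips is practical.

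**The case against.** The strongest reply is that nothing is shown to be wrong. The plan names a corrected level, a forming threshold, the programs and the search volumes, and use of 3dFWHMx means that smoothness was estimated from data. A reader might infer that the published clusters are false positives, or that p < 0.005 invalidates the correction. The documents support neither: they do not say that a Gaussian shape was used on long-tailed noise, and with Gaussian noise and matched smoothness the method was conservative at this same forming threshold.

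The second reply also stands. In the masks, which supply the regions, the mild-tail results on the acquisition grid and the 10% smoothness results are compatible with 5%. Clear excess needs a heavier assumed tail, or the 2 mm grid with the larger assumed mask. Applying the 0.16-0.25 figures to the region-defining maps would be a mistake, since they belong to Figure 3. Nor do the simulations show that the later coherence tests are inflated.

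Third, smoothness, extent and sidedness may be reported in the Results, which are not in the supplied text. Their absence here is missing detail, not an error. Reporting them would settle disclosure but leave the level dependent on the noise model.

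Fourth, the remedy has limits. Sign-flipping was not tested on the 2 mm grid or as a correction across several maps. With an assumed 0.5 SD period shift and 12/11 visit ordering it became conservative (0.005, 95% CI 0.001-0.015).

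**Conclusion.** The point holds as a cheap improvement. The 5% level is nominal only if two unverified inputs, smoothness and noise shape, are right. Over the assumed range, error in the masked maps ran from about 0.01-0.03 (Gaussian) through about 0.05 (mild tail, acquisition grid) to about 0.08-0.15 (heavy tail). Sign-flipping on the acquisition grid stayed at 0.02-0.07, within Monte Carlo error of 5% or below it, without using either input.

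These figures are illustrations, not bounds. They rest on assumed mask volumes, smoothness, tail shapes and clustering rules, with a Monte Carlo standard error of about 1-3 percentage points. Confidence that a change is worth making is moderate. Whether the actual maps are affected cannot be told from the documents.

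**What to change.** For each map that is a tolcapone-minus-placebo contrast, set the cluster extent by max-cluster sign-flip permutation of the within-subject difference maps. This covers Figure 3 (whole brain) and, where they are drug contrasts, Figures 4 and 5a (AAL 3-32 and 71-76) and Figure 5b (AAL 3-32). Keep the forming threshold of p < 0.005, apply the same threshold to Figure 5b, and state one sidedness throughout. If any map is in fact a correlation with a covariate, permute the covariate instead; the supplied text does not describe such a voxelwise map.

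Report whether the Figure 4a putamen and Figure 5b cingulate clusters survive, and interpret the coherence analysis accordingly. State the estimated smoothness, noise model and extents for the existing correction.

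The cost is computing time on existing maps. Clusters may be lost, or gained where the simulated extent was conservative. Sign-flipping assumes differences symmetric about zero under the null and can be conservative if there is a period effect; re-randomising visit order within the counterbalancing, or modelling period, addresses that.

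### Does task coherence need a repeat in atlas-defined regions because its two regions came from the same cohort's own maps?

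*Combined protocol and SAP*

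**What the plan says.** The coherence regions are reached in three steps.

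1. **Seed.** Under Multivariate analysis (resting-state paragraph): "A striatal region of interest in the left ventral putamen was chosen, based on the results of our univariate analyses (see Results, Figure 4a"). Under Univariate analysis, "subsequent univariate analyses designed to address more specific task-related hypotheses about changes in frontostriatal regions used the AAL template brain" to build a frontostriatal mask ("AAL areas 3-32 and 71-76; analyses illustrated in figures 4 and 5a"). Figure 4 is thus tied to task hypotheses, so the seed most likely comes from the task runs.
2. **Target.** The seed's time course was correlated with the rest of the brain in resting scans from 22 of the 23 subjects. Before group inference, "data were masked with a prefrontal mask (AAL regions 3-32) before the appropriate cluster-size correction was calculated". The stated purpose was drug-related change: "This approach allowed us to identify any drug-related changes in connectivity independent of task performance".
3. **Coherence.** In the task-connectivity paragraph, "we used the seed region (left ventral putamen) and significantly-connected region (left pregenual anterior cingulate cortex) identified in the resting state connectivity analysis". Coherence is then computed from the eight task runs, and the use named for it is correlation: "To compute correlations between coherence results and other values, we first Fisher-transformed the coherence values".

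The AAL template appears only as a search mask. The available text describes no coherence analysis in regions defined without the study's maps.

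**The concern.** Both regions were located with data from the cohort in which coherence is then measured. If a region is chosen because it shows a large drug effect, and a related effect is then tested in the same people, part of the second result can be carried over from the first. The seed is the closer case, since its selection and the coherence calculation probably share the task runs.

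Two things would be at stake. A reader might count the resting-state and task results as two separate confirmations of one circuit. The p-values for coherence might also be too small. Repeating coherence in regions outlined by the AAL template, which the study already uses, looks like a cheap safeguard.

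**Working it through.** The documents give no error rate or power for coherence, so there is no planned figure to reproduce. The check asks when the selection could distort the coherence test, and by how much.

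**Inputs from the documents.** N = 22 (resting-state paragraph); voxel threshold p < 0.005 and map-wise 5% (Univariate analysis).

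**Assumptions.** Subject-level drug differences are normal. The target is the largest of K = 30 independent candidates, kept if it passes the cut. The task difference in that region is y = ρx + √(1 − ρ²)e, where x is the resting difference and e is independent noise. There is no true task effect, and ρ ranges from 0.2 to 0.7. A 5% map-wise level means a per-candidate cut of 1 − 0.95^(1/30) = 0.00171. Cluster extent is not modelled.

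**Reading closest to the text: mean selected, correlation tested.** The purpose of the resting analysis and the t-test program named under Statistical Analysis point to selection on a mean drug difference. The use named for coherence is a correlation with other values. Under the null, the other measure is unrelated to the imaging data. A selection made without that measure cannot create a correlation with it. Simulated error of a nominal 5% test at ρ = 0.2 / 0.3 / 0.5 / 0.7:

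| Cut | Error |
|---|---|
| p < 0.005 | 0.047 / 0.051 / 0.053 / 0.049 |
| map-wise 5% | 0.046 / 0.048 / 0.049 / 0.052 |

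All are 5% within simulation error. With the seed also selected on a mean, the result is 0.049 to 0.053.

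**Less favourable reading: mean selected, mean tested, chance target.**

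| Cut | Error at ρ = 0.2 / 0.3 / 0.5 / 0.7 |
|---|---|
| p < 0.005 | 0.083 / 0.125 / 0.291 / 0.544 |
| map-wise 5% | 0.085 / 0.137 / 0.310 / 0.643 |

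Correlation selected and correlation tested gives nearly the same values. A separate run with K = 50 and 100 at p < 0.005 gives 0.12, 0.27–0.28 and 0.56 at ρ = 0.3, 0.5 and 0.7, so K matters little. At ρ = 0 the error is 0.04–0.05, and for a region fixed in advance it is 0.049.

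These rates are conditional on a false target having been found. At the map-wise level that happens in 5% of null studies. A false target and a false coherence result together therefore occur in 0.05 × 0.085 = 0.4% of null studies at ρ = 0.2, and in 0.05 × 0.643 = 3.2% at ρ = 0.7. Two independent tests would give 0.05 × 0.05 = 0.25%.

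**Same pairing, but with one real resting effect (p < 0.005).** A standardized effect of 0.6 gives 0.060 / 0.068 / 0.107 / 0.165. An effect of 1.0 gives 0.053 / 0.050 / 0.054 / 0.060.

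**Seed alone, mean selected and mean tested.** With six striatal areas searched and a correlation of 0.2 / 0.3 / 0.5 between the activation and coherence differences, error is 0.086 / 0.125 / 0.285.

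**What an atlas repeat would buy.** Suppose a focal effect d = 0.8 fills a share f of the atlas signal, and the rest has no effect, the same SD, and correlation c (0 to 0.8) with the focal part. Then d′ = f·d / √(f² + (1 − f)² + 2f(1 − f)c). Power comes from the noncentral t with 21 degrees of freedom and noncentrality d′√22.

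| f | d′ (c = 0 to 0.8) | Power |
|---|---|---|
| 1 (focal) | 0.80 | 0.947 |
| 0.75 | 0.759 to 0.624 | 0.92 to 0.80 |
| 0.50 | 0.566 to 0.422 | 0.72 to 0.47 |
| 0.25 | 0.253 to 0.208 | 0.20 to 0.15 |

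The labels would still be named after seeing the maps, so bias would not vanish under the less favourable reading. If atlas and focal coherence differences correlate 0.8, the single-candidate error at ρ = 0.3 / 0.5 / 0.7 falls from 0.125 / 0.280 / 0.550 to 0.100 / 0.187 / 0.344.

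**The case for a change.** The strongest case for acting is that the facts are not in dispute. Both regions are data-derived in one cohort, the seed probably from the task runs that coherence uses, and the available text describes nothing that would let rest-task agreement be read as replication. The template and the normalization already exist, so one more pair of regions costs little. A positive result there would show that the finding does not hinge on where the maps placed the regions.

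Part of this stands: coherence is conditional on the selection, and agreement between the two analyses should not be counted as two fully independent results. The rest does not carry over to a change.

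- The text describes coherence as an evaluation of connectivity during the task and never calls it replication.
- The target was selected on resting scans and tested on other runs, so its scan noise is not reused. Dependence runs through the shared subjects and an unknown ρ.
- An atlas repeat would use the same subjects, so it could not supply independence.
- It would replace the circuit identified at rest with whole anatomical labels, and a null result would not be decisive.
- The documents give AAL area numbers only. They do not show that any label matches the ventral putamen or pregenual cingulate.

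Functional regions and template regions are both defensible, and the choice between them here is a matter of preference.

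**Conclusion.** No change to the plan. No stated rule is shown to give a wrong result. On the reading closest to the text, the coherence test keeps its 5% error at every ρ examined. Higher error needs three things together: selection and test on the same kind of statistic, a rest-task correlation well above zero, and a target that is a chance finding or only a moderate real effect. Even then the range is wide (about 8% to 64% for a chance target, 5–6% with a real resting effect of 1.0), and it depends on a ρ that the documents do not report.

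This rests on two inferences: that the target was picked on a mean drug difference, and that coherence was tested by correlation. Figures 4a and 5b are not available here, so the selection contrasts cannot be confirmed, nor can it be excluded that a robustness check appears in the Results. If a region was picked by its correlation with the same measure later correlated with coherence, the less favourable figures become the relevant ones.

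What remains is a point of interpretation: task coherence describes the circuit selected from group maps in this cohort and is not a fully independent replication of the resting-state result. The primary behavioural outcome does not depend on it.

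### Task-state putamen–cingulate coherence is described without the movement, white-matter and ventricular regression used for the resting data, so shared nuisance signal can inflate it; the frequency band is also not given.

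*Combined protocol and SAP*

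**What the plan says.** All references are to the Combined protocol and SAP.

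- **Multivariate analysis, task-state paragraph.** It opens "For the evaluation of connectivity during task performance" and takes two regions from the resting-state result: the left ventral putamen and the left pregenual anterior cingulate. Each of the eight runs is "windowed with a 4-point split-cosine bell and concatenated with the other segments to produce a subject-specific time series". Voxels are averaged and coherency is estimated "using a 64-point discrete Fourier transform, Hanning window, and overlap of 32 points". Then: "Coherence values for each ROI were then computed using the band-averaged coherence". No lower or upper frequency is given, and no regression or temporal filter is listed.
- **Use of the result.** "To compute correlations between coherence results and other values, we first Fisher-transformed the coherence values". The other quantities are not named, and this paragraph states no tolcapone-versus-placebo test of coherence.
- **Multivariate analysis, resting-state paragraph.** The resting series had "temporal bandpass filtering between 0.009 Hz and 0.08 Hz to reduce the influence of cardiac and respiratory artifact", and "Movement parameters and the white matter and ventricular time series, but not the global mean signal, were included as regressors of no interest". The wording ties both steps to the resting data.
- **fMRI preprocessing.** The steps listed are slice timing, realignment, smoothing, co-registration and normalization. There is no nuisance regression and no temporal filter.
- **Univariate analysis.** The task model involves "modeling the cue and decision phases of the task for the four different conditions". Nothing says that residuals from this model were passed to the coherence analysis.

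**The concern.** Coherence between two regions rises with any signal they share in phase, whatever its source. Realignment does not remove residual movement-related signal, and it does nothing about cardiac or respiratory fluctuation. The authors recognised this for the resting data, where they regressed out movement, white-matter and ventricular series. For the task data, with the same regions and scanner, the text lists no such step.

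Two uses of the result are exposed. The level of coherence could be partly nuisance signal. Correlations across subjects between coherence and other measures could partly reflect who moved more or had larger physiological fluctuation. A within-subject design does not protect correlations across subjects.

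The missing band limits make this worse. The coherence cannot be reproduced from the text, and the weight of any shared signal depends on which frequencies were averaged.

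**Working it through.** The documents give no coherence figure, so there is none to reproduce. What can be checked is the spectral arithmetic and the mechanism.

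**1. What the stated settings imply.** TR = 1.37 s (MRI image acquisition); 64-point transform (Multivariate analysis).

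- Bin width = 1/(64 × 1.37) = 0.0114 Hz. Nyquist = 1/(2 × 1.37) = 0.365 Hz. There are 32 non-zero bins.
- The resting filter of 0.009–0.08 Hz would keep bins 1 to 7 (0.0114 to 0.0798 Hz), that is 7 of 32. The task paragraph does not say that this filter applies.

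**2. Shared nuisance signal: simulation.** Assumed, not in the documents: background AR(1) noise (0.4) correlated 0.4 between regions; a shared slow nuisance signal (AR(1), 0.9) of the same sign in both; 5% or 10% nuisance share; 0.009–0.08 Hz; runs demeaned; eight runs of 313 volumes (32 trials of about 13.4 s). The 32 per run is 256/8 and assumes an even split. Two hundred simulated subjects per setting; standard error at most 0.003.

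| Squared coherence | 5% share | 10% share |
|---|---|---|
| No nuisance regression | 0.200 | 0.239 |
| Same, nuisance amplitude +30% in both regions | 0.225 | 0.287 |
| After regression, regressor exact (with or without +30%) | 0.162 | 0.162 |
| After regression, regressor reliability 0.7 | 0.173 | 0.185 |
| Same, with +30% | 0.180 | 0.201 |

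A separate simulation gave 0.202 and 0.242 for the first row and about 0.16 after regression.

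**3. Check by hand.** With background correlation ρ = 0.4, and q the in-band ratio of nuisance to background power, pooled coherence is C = [(ρ + q)/(1 + q)]².

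- At q = 0, C = 0.4² = 0.16.
- From C = 0.200: √C = 0.4472, so q = (0.4472 − 0.4)/(1 − 0.4472) = 0.0854. From C = 0.239: √C = 0.4889, so q = 0.0889/0.5111 = 0.174.
- Amplitude +30% multiplies q by 1.3² = 1.69. Then q = 0.144 gives (0.544/1.144)² = 0.226, and q = 0.294 gives (0.694/1.294)² = 0.288. The simulation gave 0.225 and 0.287.
- Reliability 0.7 leaves 0.3 of q. Then q = 0.0256 gives (0.4256/1.0256)² = 0.172, and q = 0.0522 gives (0.4522/1.0522)² = 0.185. The simulation gave 0.173 and 0.185.

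The table therefore follows from the assumed shares.

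**4. Dependence on the band.** In a separate illustration with no true coupling, white noise and an identical evoked signal at 20% of variance in both regions, coherence was 0.144 (8 s trial spacing) or 0.201 (12 s) in 0.009–0.08 Hz, against 0.035 or 0.040 over all bins. The ratios are 0.144/0.035 = 4.1 and 0.201/0.040 = 5.0.

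**5. Evoked signal and what task regression can do.** Using the background noise and band of step 2, with evoked rather than nuisance signal and same-sign responses in both regions, raising the seed's evoked part by 30% moved coherence from 0.266 to 0.290 at a 10% evoked share and from 0.369 to 0.408 at 20%. With opposite-sign responses at 10% it moved from 0.023 to 0.009, so the direction is not fixed.

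Task regression returned 0.163 throughout only because the simulated response matched the regressor exactly. With an assumed 50% trial-to-trial amplitude variation, residual coherence still moved from 0.210 to 0.223 (10%) and from 0.265 to 0.289 (20%). The remaining shifts are 0.013 of 0.024 and 0.024 of 0.039, more than half in each case.

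**The case against.** **The text is condensed, and steps may have been done without being reported.** This stands. The paragraph also omits removing each run's mean. Tapering runs with an assumed baseline of 20 or 100 noise standard deviations, without removing the mean, gave coherence of 0.996 or more whatever the coupling, so the literal sequence is unlikely to be complete. The coherency method is also attributed to an earlier paper, which may give the band or preprocessing; the documents do not reproduce either. The point therefore concerns the analysis as described. If the steps were done, a sentence settles it.

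**Shared task response is a legitimate part of connectivity during a task.** This also stands. A reader might infer that leaving evoked responses in the series is an error. The documents do not support that: the paragraph claims connectivity during performance, not coupling beyond the shared response. Coherence after task regression is a different quantity.

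**A reader might infer that a drug effect on coherence is an artefact of tolcapone changing the evoked response.** The documents do not support this either. The Univariate analysis section reports widespread drug-related BOLD change, but that does not show a changed evoked response in either region. Rescaling a whole series leaves coherence unchanged. No drug contrast of coherence is stated in the task paragraph.

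**The sizes are assumed.** Correct. The nuisance and evoked shares, background correlation, trial length and 30% changes are not in the documents.

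None of this answers the asymmetry within one section: nuisance regression is stated for rest and not for task, with no reason given.

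**Conclusion.** The concern holds for nuisance signal. As described, the task-state coherence lacks a correction that the same section applies to the resting data, and shared motion or physiological signal can then inflate it and affect its correlations with the unnamed measures. Under the assumptions above, the inflation is about 0.04 (0.200 − 0.162) at a 5% nuisance share and about 0.08 (0.239 − 0.162) at 10%. These figures show the mechanism and assume nuisance signal of the same sign in both regions; they do not estimate the bias in this trial.

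The missing band limits are a reporting gap. A band was evidently used, since the averaging is stated, but its limits are not.

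The evoked-signal question is partly a choice of estimand and supports no more than an optional sensitivity analysis.

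**What to change.** 1. For each task run, before the taper and concatenation, remove the run mean and regress out the movement, white-matter and ventricular series, as for the resting data. If this was already done, say so.
2. Give the lower and upper limits in Hz of the band used for the averaged coherence.
3. Optionally, report beside it the coherence after also regressing out the cue and decision regressors from the Univariate analysis section. Label it a sensitivity analysis: it targets background coupling rather than total task coupling. Because it removes evoked signal only in part when response amplitude varies between trials, agreement between the two results would not rule out shared evoked signal.

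The cost is a short re-analysis of existing data, with no new scanning. Coherence may come out lower, and imperfect regressors will leave some nuisance signal behind. If the steps were already taken, the cost is a sentence or two of text.
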